4.1.1. Screening Period

The outpatient screening visit may be up to 28 days prior to enrollment. Individuals who are not enrolled within 28 days of screening may be subjected to an additional medical assessment and/or clinical measurements to confirm their eligibility. Parameters that may be repeated for screening include clinical laboratory tests, ECGs, and vital signs.

4.1.2. Treatment Period

Study participants will be admitted to the CRU on Day -1 and adhere to an overnight fast.

Participants will be randomly assigned to treatment, followed by dosing while inpatient at the CRU. Participants will receive 3 consecutive once-daily doses of either LY3493269 or placebo on Days 1 through 3. Fasting requirements including food and water restrictions must be adhered to for each dose administered (Section 6.1.1). Participants should complete the study assessments and procedures planned during this period as specified in Section 1.3. Unless the investigator identifies a safety concern, participants may be discharged from the CRU on Day 5.

Pharmacokinetic and PD sampling and safety assessments will be performed according to the SoA (Section 1.3). Pharmacokinetic and PD sampling schedules may be modified based on the available safety and PK/PD data.

4.1.3. Outpatient Visits (Days 6, 8, and 15)

Participants will return to the CRU for outpatient visits on Days 6, 8, and 15, for safety assessments and PK and/or PD sampling at the times specified in the SoA (Section 1.3). Participants may remain as needed at the CRU for safety monitoring based on the investigator's judgment or to facilitate participant compliance.

4.1.4. Follow-Up Visits (Days 29 and 43)

During the follow-up period, participants should attend the outpatient visits on Days 29 and 43. The study assessments and procedures planned during this period should be performed as specified in the SoA (Section 1.3).

Participants who received study intervention and who discontinue early will be encouraged to return for an early termination visit with procedures performed as shown in the SoA (Section 1.3) and a follow-up visit for safety monitoring, including but not limited to 28 days after study intervention. Enrolled participants who discontinue without study intervention will not be required to attend the early termination visit.

Participants will be discharged from the study after the investigator has completed review of all final safety assessments from the last follow-up visit.

4.2. Scientific Rationale for Study Design

A population of healthy participants is selected to assess the safety and tolerability of LY3493269 for initiation of oral administration in humans prior to further investigations in participants with T2DM. Using a healthy participant population mitigates possible confounding effects of comorbidities and concomitant medications. Therefore, Study GZHF provides an unbiased assessment of safety, tolerability, and PK of LY3493269 administered as oral doses.

The study is intended to estimate a maximum tolerated exposure or establish that exposures exceeding the expected therapeutic range are tolerated via the oral route of administration. Additionally, the study will inform the target exposure range for subsequent oral dosing of LY3493269. Safety, tolerability, PK, and preliminary PD data will assist in identifying an appropriate dose range for subsequent clinical studies regardless of administration route.

A study design of once-daily oral dosing for 3 days will be employed to characterize oral PK behavior of LY3493269. The dosing duration of 3-days was selected after taking into consideration the following factors:

- low oral bioavailability expected from oral peptide formulations,
- the exceptionally high inter- and intra-individual variabilities in oral bioavailability expected of oral peptide formulations,
- the sensitivity of the bioanalytical assay, and
- once absorbed via the oral route of administration, LY3493269 systemic PK disposition should be similar regardless of route of administration, hence safety, tolerability, and PK data from the SC SAD study (GZHA) should be applicable to this study.

To predict the oral PK profiles for each cohort, extensive PK simulations were conducted. The PK profile following a single oral dose was deemed to be at risk of being highly variable and potentially returning lower than quantifiable concentrations at multiple time points. The simulation results did suggest that 3 days was adequate for a majority of PK profiles from participants in each cohort to remain above the quantification limit of CCI to yield meaningful PK results. The PK data from Study GZHA estimated the LY3493269 CCI . Therefore, PK exposures from a short dosing duration of 3 days from this study are not expected to reach steady state for the respective doses.

Strict oral administration conditions such as controlling the duration of fasting before and after dosing and water volume for oral administration of LY3493269 will be imposed. These are necessary to reduce any potential variability arising from oral administration conditions that may affect oral bioavailability of LY3493269.

Safety and tolerability assessments will be made across all dose levels, including incidence of nausea and/or vomiting, and evaluation of ECGs and vital signs conducted during the study (Section 8.2). A preliminary assessment of the PD effects of LY3493269 will be based on the concentrations of fasting glucose, insulin, and triglycerides up to Day 29 postdose. The effect of LY3493269 on appetite sensations will also be explored. The decision to escalate the dose will be based primarily on safety and tolerability data (Sections 6.6.1 and 6.6.2) and all available PK data will also be reviewed.

4.3. Justification for Dose

The proposed LY3493269 oral dose range of 8 to 48 mg once daily is selected to attain steady-state exposures anticipated to be within the range equivalent to the Phase 3 dose range (SC 5 to 15 mg once weekly) of another GIP-GLP-1 molecule currently in Phase 3 development (tirzepatide). These doses have also been tested with no major safety concerns in another study (GZHB) where LY3493269 was dosed in combination with another permeation enhancer (C10). The equivalent LY3493269 oral doses are predicted to be between 4 and 59 mg once daily assuming CC

. If oral

0.4% to 1.0% reported for another approved oral peptide co-formulated with SNAC (Rybelsus[®] [Rybelsus (semaglutide) [package insert], 2020]) to ensure a conservative estimate of exposure multiple. Dose equivalents between the 2 molecules **CC**

bioavailability is doubled to column the anticipated average exposures of the first cohort of 8 mg once daily × 3 days are expected to be lower than the exposures from the LY3493269 SC 1.5 mg dose.

Salcaprozate sodium has generally regarded as safe (GRAS) status and is contained in FDA-approved medical food (Eligen®-Vitamin B12, Emisphere, Roseland, NJ, USA). Rybelsus® tablet, which is approved by FDA, European Medicines Agency and Japan Pharmaceuticals and Medical Devices Agency, contains SNAC at 300 mg. In addition, in a first-in-human trial, up to 600 mg SNAC was evaluated with oral semaglutide with no safety concerns reported (Granhall et al. 2019). Cohort 4 is intended to assess if half the amount (300 mg) of SNAC can yield comparable oral bioavailability as 600 mg of SNAC at the same 24-mg dose of LY3493269.

All of the identified risks in Section 2.3 are considered to be reversible, monitorable, and manageable and will continue to be monitored closely in clinic. The margin of safety of oral administered LY3493269 with SNAC or SNAC alone derived from 1-month repeat-dose toxicity studies is listed in Table 4.1 and Table 4.2.

Table 4.1 Margins of Safety for Oral Administration of LY3493269 with SNAC, Based on Body Surface Area and Predicted Exposure

	Dose (mg/kg)	Dose (mg/m²)	Dose multiple ^a		C _{ave} (ng/mL) ^c	Projected exposure multiple ^d		
			Starting dose	Maximum dose		Starting Dose	Maximum dose	
Human starting dose (8 mg/day) ^b	0.114	4.218			56.6			
Human maximum dose (48 mg/day) ^b	0.686	25.38			341			
	M	ultiples De	rived from l	PO GLP Stud	ies (QD)			
Rat NOAEL (HDT) ^e	3	18	4.27	0.709	8	0.141	0.0235	
Monkey HDT ^f	3	36	8.53	1.42	1194	21.1	3.5	
Monkey LOAEL (LDT) ^f	1	12	2.84	0.472	546	9.65	1.60	
Exposu	re Multiple	es Derived	from SC GI	LP Studies (Ra	at: BIW; Mo	nkey: QW)	i	
Rat NOAEL ^g	0.05	0.3			83.5	1.48	0.245	
Rat HDT ^g	1	6			1604	28.3	4.70	
Monkey NOAEL ^h	0.05	0.6			356	6.29	1.04	
Monkey HDT ^h	1	12			7440	131	21.8	

Abbreviations: AUC = area under the plasma concentration versus time curve; BIW= twice weekly dosing; C_{ave} = average drug concentration during the dosing interval for a single dose; GLP = glucagon-like-peptide; HDT = highest dose tested; LDT = lowest dose tested; LOAEL = lowest-observed-adverse-effect level; NOAEL = no-observed-adverse-effect level; QD = once daily dosing; QW = once weekly dosing; SC = subcutaneous.

- a Dose multiple (based on body surface area) is calculated as dose in animals (mg/m²)/dose in humans (mg/m²).
- b Typical body weight of 70 kg was assumed for a healthy subject. AUC₀₋₂₄ following the last dose based on assumed CC
- c C_{ave} was calculated based on AUC_{0-t} normalized by dosing interval.

H: C_{ave} was calculated with plasma AUC₀₋₂₄, based on preliminary PK exposure data from Study GZHA, from time 0 to 24 hours after the last (3rd) oral daily dose assuming CCl relative to SC administration, divided by 24 hr.

Rat and monkey oral QD: C_{ave} was calculated based on observed plasma AUC_{0-24} on Day 28, divided by 24 hr. Rat SC: C_{ave} was calculated based on observed plasma AUC_{0-96} on Day 29, divided by 96 hr.

Monkey SC: Cave was calculated based on observed plasma AUC₀₋₁₆₈ on Day 29, divided by 168 hr.

- d Exposure multiple is the calculated Cave in animals/predicted Cave in humans;
- e Rat NOAEL (HDT) of LY3493269 (with 600 mg/kg SNAC) was determined in a 1-month repeat-dose toxicity study via oral gavage (130-843).
- f Monkey HDT and LOAEL (LDT) of LY3493269 (with 600 mg/kg SNAC) was determined in a 1-month repeatdose toxicity study via oral gavage (20235767).
- g Rat NOAEL and HDT was determined in a 1-month repeat-dose toxicity study via subcutaneous injection (130-735).
- h Monkey NOAEL and HDT was determined in a 1-month repeat-dose toxicity study via subcutaneous. injection (130-739).
- i Dose multiple was not calculated due to assumed low oral bioavailability of LY3493269.

Table 4.2 Margins of Safety for oral Administration of SNAC, Based on Body Weight and Predicted Exposure

	Dose (mg/kg)	Dose (mg/m²)	Dose multiple ^a	AUC (0-t) (ng.hr/mL)	Projected exposure multiple ^d
Human dose (600 mg/day) ^b	8.57	317		2258 ^C	
Rat NOAEL ^e	600	3600	11.4	36800	16.3
Monkey NOAEL f	600	7200	22.7	319000	141

Abbreviations: AUC = area under the plasma concentration versus time curve; HDT= highest dose tested; NOAEL = no-observed-adverse-effect level.

- a Dose multiple (based on body weight, given the effect of SNAC expected to be local) is calculated as dose in animals (mg/kg)/dose in humans (mg/kg).
- b Typical body weight of 70 kg was assumed for a healthy subject.
- c Human plasma AUC of SNAC was estimated using published SNAC AUC(0-24) at the dose of 300 mg, assuming dose proportional increase of AUC from 300 to 600 mg (Bækdal TA, et al. Expert Opinion on Drug Metabolism & Toxicology 2018).
- d Exposure multiple is the observed AUC in animals on Day 28/published AUC in humans.
- e Rat NOAEL of SNAC was determined in a 1-month repeat-dose toxicity study (130-843). It is the mean Male +Female from Study 130-843, Day 28 toxicokinetic data.
- f Monkey NOAEL of SNAC was determined in a 1-month repeat-dose toxicity study (20235767). It is the mean Male +Female from Study 20235767, Day 28 toxicokinetic data.

In conclusion, the safety pharmacology and toxicity assessment of oral administered LY3493269 did not reveal any adverse findings in animals. The nonclinical safety data support the proposed Phase 1 study for an oral formulation of LY3493269.

4.4. End of Study Definition

A participant is considered to have completed the study if they have completed all required phases of the study including the last scheduled procedure shown in the SoA (Section 1.3).

Any participant who does not satisfy this definition but who has completed all the key assessments may be considered a completer at the discretion of the sponsor.

The end of the study is defined as the date of the last visit of the last participant in the study.

5. Study Population

Eligibility of participants for the study will be based on the results of screening medical history, physical examination, vital signs, clinical laboratory tests, and ECG.

The inclusion and exclusion criteria used to determine eligibility should be applied at screening only, and not continuously throughout the trial.

The nature of any conditions present at the time of the physical examination and any preexisting conditions will be documented.

Screening may occur up to 28 days prior to enrollment. Participants who are not enrolled within 28 days of screening may undergo an additional medical assessment and/or clinical measurements to confirm their eligibility. Parameters repeated for screening include clinical laboratory tests, body weight, ECGs, and vital signs.

Prospective approval of protocol deviations to recruitment and enrollment criteria, also known as protocol waivers or exemptions, is not permitted.

Individuals who do not meet the criteria for participation in this study (screen failure) may not be re-screened.

5.1. Inclusion Criteria

Participants are eligible to be included in the study only if all of the following criteria apply:

Participant Characteristics

1. Are male or female not of childbearing potential from 21 to 65 years of age, inclusive, at the time of signing the informed consent.

Note: For contraception requirements of this protocol, see Appendix 4 (Section 10.4).

2. Body mass index within the range of 19.0 to 40.0 kg/m^2 (inclusive).

Type of Participant and Disease Characteristics

- 3. Participants who are healthy as determined through medical evaluation including screening medical history, physical examination, vital signs, clinical laboratory tests, and ECG.
- 4. Have clinical laboratory test results within normal reference range for the population or CRU, or results with acceptable deviations that are judged to be not clinically significant by the investigator.
- 5. Have venous access sufficient to allow blood sampling as per the protocol.
- 6. Are reliable and willing to make themselves available for the duration of the study and who will comply with the required study and dosing visits and abide by the clinical research site policy and procedure and study restrictions.

Informed Consent

7. Capable of giving signed informed consent as described in Appendix 1 (Section 10.1) which includes compliance with the requirements and restrictions listed in the ICF and in this protocol

5.2. Exclusion Criteria

Participants are excluded from the study if any of the following criteria apply:

Medical Conditions

- 1. Have a history of atopy (severe or multiple allergic manifestations) or clinically significant multiple or severe drug allergies, or intolerance to topical corticosteroids, or severe posttreatment hypersensitivity reactions (including, but not limited to, erythema multiforme major, linear immunoglobulin A dermatosis, toxic epidermal necrolysis, anaphylaxis, angioedema, or exfoliative dermatitis)
- 2. Have a significant history of or current CV (for example, myocardial infarction, congestive heart failure, cerebrovascular accident, venous thromboembolism, etc.), respiratory, renal, GI, endocrine, hematological (including history of thrombocytopenia), or neurological disorders capable of significantly altering the absorption, metabolism, or elimination of drugs; of constituting a risk while taking the IP; or of interfering with the interpretation of data
- 3. Have a supine HR less than 45 bpm or greater than 100 bpm. If a repeat measurement shows values within the range, the participant can be included in the trial.
- 4. Have a mean supine systolic BP higher than 160 mmHg and a mean supine diastolic BP higher than 95 mmHg from 2 assessments at screening; therefore, if a repeated measurement shows values within the range, the participant can be included in the trial.
- 5. Have undergone any form of bariatric surgery.
- 6. Have a history of GI bleeding or duodenal ulcers.
- 7. Have a personal or family history of medullary thyroid carcinoma or have multiple endocrine neoplasia syndrome type 2.
- 8. Have a history of acute or chronic pancreatitis, or elevation in serum lipase and/or amylase levels greater than 1.5 times the ULN.
- 9. Have clinical signs or symptoms of liver disease, acute or chronic hepatitis.
- 10. Have evidence of significant active neuropsychiatric disease as determined by the investigator.

Prior/Concomitant Therapy

- 11. Have been treated with prescription drugs that promote weight loss within 3 months prior to screening. Examples include
 - Meridia[®] (sibutramine),
 - Sanorex® (mazindol),

- Adipex-P[®] (phentermine),
- BELVIQ® (lorcaserin),
- Mysimba® (naltrexone/bupropion),
- Saxenda® (liraglutide) or
- similar other body weight loss medications including any over-the-counter medications or supplements (for example, alli®).
- 12. Have received chronic (lasting >14 consecutive days) systemic glucocorticoid therapy in the past year, or have received any glucocorticoid therapy within 1 month before screening (topical, intra-articular, and inhaled preparations such as steroid nasal spray are permitted in the study)
- 13. Intend to use over-the-counter or prescription medication within 7 or 14 days, respectively, prior to planned dosing (apart from vitamin/mineral supplements, occasional paracetamol, and thyroid replacement medication) and throughout the study period. If this situation arises, inclusion of an otherwise suitable participant may be at the discretion of the investigator and sponsor.

Prior/Concurrent Clinical Study Experience

- 14. Are currently enrolled in a clinical study involving an IP or any other type of medical research judged not to be scientifically or medically compatible with this study
- 15. Have participated within the past 30 days of screening in a clinical study involving an IP; at least 5 half-lives or 30 days, whichever is longer, should have passed

Diagnostic assessments

- 16. Have an abnormality in the 12-lead ECG at screening that, in the opinion of the investigator, increases the risks associated with participating in the study or may confound ECG (QT) data analysis, such as a QTcF >450 msec for males and >470 msec for females, short PR interval (<120 msec), or PR interval >220 msec, second and third atrioventricular block, intraventricular conduction delay with QRS >120 msec, right bundle branch block, left bundle branch block or Wolff-Parkinson-White syndrome.
- 17. Have serum AST or ALT >1.5 \times ULN or TBL >1.5 \times ULN.
- 18. Show evidence of HIV infection and/or positive human HIV antibodies.
- 19. Show evidence of hepatitis C and/or positive hepatitis C antibody.
- 20. Show evidence of hepatitis B, positive hepatitis B core antibody, and/or positive hepatitis B surface antigen.

Other Exclusions

- 21. Are CRU personnel directly affiliated with this study and their immediate families. Immediate family is defined as a spouse, biological or legal guardian, child, or sibling
- 22. Are Lilly employees.
- 23. Have previously completed or withdrawn from this study.

- 24. Have donated blood of more than 450 mL, or have participated in a clinical study that required similar blood volume drawn within the past 3 calendar months.
- 25. Are women who are lactating.
- 26. Have known allergies to LY3493269, related compounds, or any components of the formulation (including SNAC), or a history of significant atopy.
- 27. Regularly use known drugs of abuse.
- 28. Have an average weekly alcohol intake that exceeds 21 units per week (males) and 14 units per week (females) or are unwilling to stop alcohol consumption as required during the study (Section 5.3.2) (1 unit = 12 oz or 360 mL of beer; 5 oz or 150 mL of wine; 1.5 oz or 45 mL of distilled spirits).
- 29. Smoke >10 cigarettes per day or the equivalent, or are unable or unwilling to refrain from nicotine during CRU admission.
- 30. Are unwilling to comply with the dietary restrictions required for this study.
- 31. In the opinion of the investigator or sponsor, are unsuitable for inclusion in the study.

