2.3. Benefit/Risk Assessment

There is no anticipated therapeutic benefit for the participants in this trial.

The sponsor has evaluated the preclinical and clinical risks associated with LY3493269. Nonclinical safety of SC LY3493269 was evaluated in a CV safety pharmacology study in monkeys and 1-month repeat-dose toxicology studies in rats and monkeys. Important LY3493269-related findings in the rat and monkey included body weight loss and/or reduced body weight gain and decreased food consumption. Additional findings from the monkey studies included changes in CV parameters (such as increases in HR and BP). In Study GZHA, similar findings were observed, which include

- nausea
- vomiting
- loss of appetite, and
- increased HR.

Salcaprozate sodium has GRAS status and is contained in FDA-approved medical food (Eligen[®]-Vitamin B12, Emisphere, Roseland, NJ, USA; Twarog et al. 2019). Rybelsus[®] tablet, which is approved by FDA, European Medicines Agency and Japan Pharmaceuticals and Medical Devices Agency, also contains SNAC (daily dose of 300 mg). In addition, in a first-in-human trial, up to 600 mg SNAC was evaluated with oral semaglutide with no safety concerns reported (Granhall et al. 2019).

In the completed nonclinical safety pharmacology and toxicology studies, LY3493269 orally co-administered with SNAC produced body weight loss and/or decreased body weight gain, and decreased food consumption, which are consistent with, or secondary to, incretin pharmacology. The effects on body weight were dose limiting and resulted in dosing suspension in monkeys. No adverse SNAC-related effects were observed up to 600 mg/kg in any of the toxicology studies/assessments. Refer to the IB for more information.

Based on the nonclinical studies, potential risks for clinical trial participants receiving orally administered LY3493269 are similar to those for participants receiving SC administered LY3493269 and include CV effects, GI disturbances, inappetence, and weight loss.

All identified risks from the nonclinical and clinical studies are considered monitorable and manageable at the planned oral dose range of 8 to 48 mg once daily of LY3493269. To further

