8.2.2. Vital Signs

For each participant, vital sign measurements should be conducted according to the SoA (Section 1.3) and as clinically indicated.

Vital sign measurements should be obtained before collection of blood samples (applicable for study visits).

Blood pressure and PR should be measured after at least 5 minutes in a supine position.

Note: If white-coat hypertension is suspected at screening, the participant can be included in the trial if a repeated measurement (up to 2 additional assessments) shows values within the acceptable range.

If orthostatic measurements are required, participants should be supine for at least 5 minutes and stand for at least 2 minutes. If the participant feels unable to stand, only supine vital signs will be recorded.

Unscheduled orthostatic vital signs should be assessed, if possible, during any AE of dizziness or posture-induced symptoms. Additional vital signs may be measured during each study period if warranted.

Body temperature will be measured, as specified in the SoA (Section 1.3), and as clinically indicated.

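### As printed, exclusion 4 requires both blood-pressure limits to be exceeded, so the only numeric BP limit at entry misses an isolated systolic or diastolic elevation

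*Protocol*

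**What the plan says.** Protocol Section 5.2 opens its list with "Participants are excluded from the study if any of the following criteria apply". Exclusion 4 then covers volunteers who "Have a mean supine systolic BP higher than 160 mmHg and a mean supine diastolic BP higher than 95 mmHg from 2 assessments" at screening. The same criterion adds a re-test clause: "if a repeated measurement shows values within the range, the participant can be included in the trial".

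Section 8.2.2 (Vital Signs) returns to the subject in a note on suspected white-coat hypertension. It allows as many as two further readings and admits the volunteer if a repeat "shows values within the acceptable range". It gives no limits of its own.

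Three other criteria bear on a volunteer with raised BP, none with a BP figure:

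- Inclusion 3 in Section 5.1 requires "Participants who are healthy as determined through medical evaluation including screening medical history, physical examination, vital signs, clinical laboratory tests, and ECG".
- Exclusion 2 covers those who "Have a significant history of or current CV" disorder that would pose a risk on treatment or interfere with interpretation. Its cardiovascular examples do not name hypertension.
- Exclusion 31 lets the investigator or sponsor judge a volunteer unsuitable.

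**The concern.** A numeric entry limit exists so that a safety threshold does not depend on discretion. Here the two limits are joined by *and*, so the literal rule catches only combined elevation. A volunteer with one reading well above its limit and the other at or below its limit is left to judgement. Section 5 applies the eligibility criteria at screening only, so no later numeric check would pick the case up.

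The stake is mainly safety screening. Section 2.3 names cardiovascular effects as a potential risk and reports heart-rate and BP increases in monkeys. Section 2.2.1 reports a dose-dependent heart-rate increase in humans, with three mild tachycardia events at the 1.5 mg subcutaneous dose. Section 8.3.7 makes cardiovascular events adverse events of special interest. Section 4.2 justifies healthy participants partly as a way to limit confounding by comorbidity, while Section 5.1 admits ages up to 65 and BMI up to 40, so raised BP at screening is not a remote possibility.

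**Working it through.** The plan gives no figure to reproduce. The check is a logical reading of the criterion, followed by a comparison of the related sections.

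**Step 1. The rule.** Let S mean that mean supine systolic BP is above 160 mmHg, and D that mean supine diastolic BP is above 95 mmHg (both from exclusion 4). As printed: exclude if S *and* D. The alternative reading: exclude if S *or* D. The opening line of Section 5.2 says that any one criterion excludes. That works between criteria and does not alter the connective inside this one.

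**Step 2. All four combinations.** The readings are illustrations, not data.

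| S | D | Example (mmHg) | Printed *and* | *Or* reading |
|---|---|---|---|---|
| yes | yes | 175/100 | excluded | excluded |
| yes | no | 185/90 | not excluded by criterion 4 | excluded |
| no | yes | 150/110 | not excluded by criterion 4 | excluded |
| no | no | 158/94 | not excluded | not excluded |

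The readings differ in two of the four cells, namely those with one value above its limit.

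**Step 3. The re-test clause.** Take a volunteer at 175/100 who repeats at 175/94. Under the printed rule, D is now false (94 is not above 95), so the exclusion no longer applies. Yet systolic BP is still 175 − 160 = 15 mmHg above its limit, which is hard to describe as values within a range. If the range means that each limit is met, the volunteer stays excluded. One pair of readings can thus get two answers, depending on which part of the criterion is followed.

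**Step 4. Section 8.2.2 against exclusion 4.** Exclusion 4 speaks of a repeat measurement without saying how many. Section 8.2.2 allows up to two. Both rely on a range, and neither defines one beyond the two joined limits.

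**Step 5. Other BP limits.** Sections 5.1 and 5.2 set figures for age, BMI, heart rate, pancreatic enzymes, ECG intervals and liver tests. None sets one for BP except exclusion 4. What remains is judgement under inclusion 3 and exclusions 2 and 31.

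**Step 6. Scale.** The target is 8 participants on LY3493269 per cohort (Section 9.2), so one participant is 1/8 = 12.5% of a cohort's active group. That is a share of a group, not an estimate of how many would be affected. The documents give no prevalence of isolated elevation from which to derive that.

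**The case against.** The strongest reply is that this is loose drafting with adequate backstops. Inclusion 3 is mandatory and rests partly on vital signs, exclusion 2 addresses both risk and interpretability, and exclusion 31 is open-ended. An investigator faced with 185/90 would probably use one of them. Exclusions 16 and 28 also use *and* simply to list separate limits for men and women, so exclusion 4 may be a list of that kind. Much of this stands. It means that the printed rule may not be what was meant, and that the practical risk is smaller than the literal text suggests. It does not settle the wording: in exclusions 16 and 28 no one can meet both limits, so the list reading is forced, whereas a volunteer can exceed both BP limits and both readings are open.

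Several stronger readings are tempting, and the documents do not support them:

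- A reader might infer that a volunteer with isolated hypertension would be enrolled. Only criterion 4 fails to exclude; the judgement-based criteria remain.
- A reader might take exclusion 3, "Have a supine HR less than 45 bpm or greater than 100 bpm", as proof that *or* was intended. Those are two ends of one variable and cannot both be true, so *or* is forced there and says nothing about two separate variables.
- A reader might infer a BP signal in humans. Section 2.2.1 reports no significant BP change in the subcutaneous single-dose study; the human finding is heart rate, which exclusion 3 screens separately.
- A reader might infer material damage to the vital-sign analysis. Protocol Section 9.4.2 and SAP Section 9.6.5 model change from baseline with baseline as a covariate, which partly adjusts for a high starting value. The study is not powered for hypothesis tests, and the primary endpoint is treatment-emergent adverse events.
- A reader might infer inconsistency between sites. The study is single-center.

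**Conclusion.** The point holds as a wording defect in an objective safety limit. Read literally, the only numeric BP criterion does not exclude a volunteer with just one value above its limit, and exclusion then rests on judgement. The criterion fits poorly with its own re-test clause and with the note in Section 8.2.2. This is ambiguity rather than outright contradiction, since the undefined range could be read to suit either connective.

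Its size is two of the four combinations of readings; the number of volunteers in them is unknown. The conclusion assumes that the criterion is applied as printed and does not assume that investigators would fail to use their discretion. The limits themselves are not in question: under either connective, readings up to 160/95 are admitted. The correction is worth making because cardiovascular effects are a named risk and the change is small.

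**What to change.** Reconcile Protocol Section 5.2 (exclusion 4) with the note in Section 8.2.2 so that three things agree: the connective between the two limits, what the range means, and how many repeat assessments are allowed.

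The sponsor should state which rule is intended. If each limit is meant to be met, as the re-test clause suggests, join the limits with *or* and leave the figures unchanged. If only combined elevation is meant to exclude, say so explicitly and reword the re-test clause and the Section 8.2.2 note to match. No new threshold is proposed.

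The cost is one word in exclusion 4 (or one explanatory sentence) plus a matching edit in Section 8.2.2, made by protocol amendment. Under the *or* wording there may be a few more screen failures. No statistical analysis changes.
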